6 STUDY DESIGN

6.1 OVERALL DESIGN

Tight glucose control in the ICU setting is difficult to achieve. We hypothesize that a closed loop glucose control system based on artificial intelligence will improve upon the glucose control currently achieved by open loop systems. This non-randomized Early Feasibility First in Human Study at a single study site will test the ability of a prototype closed loop glucose control system to provide safe and effective glucose control in participants with type 1 diabetes who lack endogenous insulin production, and type 2 diabetes who have insulin resistance profiles that match those of ICU patients.⁵⁸ The study will be performed in a CRC setting on two participants with type 1 diabetes and six participants with type 2 diabetes over a time period of thirty-two hours per subject. The subjects will all consume three standardized meals during the 24-hour period their blood glucose levels are being controlled by the FUSION system. Study volunteers will be recruited from the adult endocrinology clinics of Emory University and/or Grady Hospital in Atlanta. Identified subjects who have been screened and enrolled in the study will have the study completed within two weeks of enrollment. An interim data analysis is not planned.

6.2 SCIENTIFIC RATIONALE FOR STUDY DESIGN

A non-randomized Early Feasibility Study design was chosen as this represents a first in human test of this artificial intelligence based closed loop glucose control system. The main goal of the study will be to test the safety and efficacy of the FUSION closed loop glucose control system, as measured by the percent of glucose values less than 70 mg/dL (safety), and the percent of glucose values in the range of 70-180 mg/dL (efficacy). Testing in the CRC setting was chosen as it is a highly monitored environment, and the subjects can be carefully chosen based on inclusion/exclusion criteria.

6.3 JUSTIFICATION FOR DOSE

For safety reasons the maximal allowed insulin dose (e.g., NovoLog) will be 0.5 units/kg/hour and the maximal dextrose (D10NS) infusion rate will be 4 mL/kg/hour, except during periods of dextrose boluses, when the maximal infusion rate will be 6.25 mL/kg/hour over a 5-minute period. These limits are consistent with a similar prior study.⁷¹

6.4 END OF STUDY DEFINITION

A participant is considered to have completed the study if he or she has completed all phases of the study including the last visit or the last scheduled procedure shown in the Schedule of Activities (SoA), Section 1.3.

The end of the study is defined as completion of the last visit or procedure shown in the SoA in the trial globally.

7 STUDY POPULATION

7.1 INCLUSION CRITERIA

A. Participants with type 1 and type 2 diabetes are eligible to be included in the study only if they meet all the following criteria:

1. Are 18-70 years of age, inclusive.
2. Can understand and sign an informed consent, communicate with the investigator, and understand and comply with the protocol requirements.
3. Have had a diagnosis of type 1 or type 2 diabetes for a period of at least 1 year.
4. Use insulin injections at home for glucose control and are on a stable insulin regimen without more than a 20% change in their total daily insulin dose during the previous 3 months. Their total daily insulin dose during the previous 3 months will be confirmed through a review of the subject's electronic health record, insulin prescriptions, and insulin pump settings (if applicable).

5. Have a hemoglobin A1c (HbA1c) in the range of 7.0 – 10.0%.
6. Have a hemoglobin in the normal range for sex:
 - a. Females: 12-15.5 grams/dL.
 - b. Males: 13.5–17.5 grams/dL.
7. Have adequate venous access sites in upper extremities.
8. Body weight between 40 – 150 kg.

7.2 EXCLUSION CRITERIA

- A. Subjects will be excluded from the study if they meet any of the following criteria:
 1. Have participated in an interventional medical, surgical, or pharmaceutical study within 30 days of screening.
 2. Have a known hypersensitivity to any of the components of study treatment.
 3. Have skin disease/injury at Dexcom G6 CGM insertion site(s) that would prevent insertion of the CGM.
 4. Currently abuses drugs or alcohol or has a history of abuse that in the investigator's opinion would cause the individual to be noncompliant.
 5. Have a medical condition that in the opinion of the investigator could affect study participation and/or personal well-being.
 6. Have a clinically significant history or presence of any of the following conditions:
 - a. Hepatic failure or has alanine aminotransferase (ALT) greater than 3 times the upper limit of normal.
 - b. Has an estimated GFR <60 ml/min/1.73 m² or End Stage Kidney Disease on renal replacement therapy.
 - c. Type 2 diabetic subjects who have a C-peptide level less than 0.2 nmol/L (these subjects will be referred to their primary care doctor or endocrinologist for further work up).
 - d. Have congestive heart failure of class 1 or greater on the NYHA classification system.
 - e. Have a history of seizures.
 - f. Have a history of cerebrovascular accident.

DEMONSTRATION OF AN ARTIFICIAL INTELLIGENCE BASED CLOSED LOOP GLUCOSE CONTROL SYSTEM AS A THERAPEUTIC MODALITY IN TYPE 1 AND TYPE 2 DIABETIC PATIENTS

Protocol IMT 2022-1

CONFIDENTIAL

Version1.0.7

22 August 2022

- g. Have a history of ischemic heart disease.
- 7. For female subjects of potential childbearing age (age 18 to 55) they will be excluded if:
 - a. Pregnant.
 - b. Refuse to agree to a pregnancy test at the time of enrollment.
 - c. Have a positive urine pregnancy test at the time of enrollment.
- 8. Have a positive COVID-19 test within 14 days of visit 3.
- 9. Have any COVID-19 related symptoms in the 14-day period prior to visit 3.
- 10. Have a known unprotected COVID-19 exposure in the 14-day period prior to visit 3.

7.3 LIFESTYLE CONSIDERATIONS

Not applicable.

7.4 SCREEN FAILURES

Screen failures are defined as participants who consent to participate in the clinical trial but are not subsequently entered in the study. A minimal set of screen failure information is required to ensure transparent reporting of screen failure participants, to meet the Consolidated Standards of Reporting Trials publishing requirements and to respond to queries from regulatory authorities. Minimal information includes demography, screen failure details, eligibility criteria, and any serious adverse event (SAE).

Individuals who do not meet the criteria for participation in this trial (screen failure) because of a failure to meet all inclusion and exclusion criteria will not be rescreened for participation in the trial.

7.5 STRATEGIES FOR RECRUITMENT AND RETENTION

Participants with type1 and type 2 diabetes will be recruited from the Diabetes Center at Grady Hospital and adult endocrinology clinics at Emory Healthcare, located in Atlanta, Georgia. All adult type 1 and type 2 diabetic patients being cared for in these clinics will be screened for inclusion in the study. The original screening will include age, weight, length of diagnosis of diabetes, use of insulin in the home setting, and their most recent HbA1c level. Potential subjects who pass these criteria will then be assessed for exclusion criteria. Potential subjects who pass the exclusion criteria will be approached for participation in the study. Willing participants will be scheduled for enrollment during visit 2. Subjects

who sign an informed consent during visit 2 will have blood drawn to evaluate their hemoglobin, HbA1c, ALT, creatinine, and C-peptide (type 2 diabetic subjects) levels. Female subjects aged 18-55 inclusive who have signed an informed consent will also have a urine pregnancy test performed during visit 2. It is anticipated that 500 adult type 1 and type 2 diabetic subjects will need to be screened to yield 8 subjects for participation in the study. It is expected that the inclusion criteria will eliminate 97% of potential enrollees. It is expected that the exclusion criteria will eliminate another 30% of the remaining potential enrollees. Study participants will be compensated for participation in the study.

8 STUDY INTERVENTION

8.1 STUDY INTERVENTION(S) ADMINISTRATION

8.1.1 STUDY INTERVENTION DESCRIPTION

8.1.1.1 COMPONENTS OF CLOSED LOOP GLUCOSE CONTROL SYSTEM

1. Two complete Dexcom G6 continuous glucose monitoring systems – Glucose sensor, Transmitter, and Receiver
2. Two mobile phones with the Dexcom G6 Follow App
3. One Medical Computer and associated power cord
4. One Powered Medical Cart and associated power cord
5. Two KDS Legato 100 syringe pumps and associated power cords
6. Two serial data cables to attach syringe pumps to Medical Computer
7. Two serial data cables to attach Dexcom G6 Receivers to Medical Computer

8.1.1.2 VISIT 1, SCREENING

This screening visit includes evaluating the medical history, comprising preexisting conditions and concomitant medications of type 1 and type 2 diabetic subjects being seen at the Diabetes Center at Grady Hospital and the adult endocrinology clinics of Emory Healthcare, located in Atlanta, Georgia. Those subjects who meet study inclusion criteria, and who do not meet any study exclusion criteria, will be approached for participation in the study. Willing participants will be scheduled for visit 2, for purposes of obtaining an informed consent and enrolling them in the study.

8.1.1.3 VISIT 2, ENROLLMENT

DEMONSTRATION OF AN ARTIFICIAL INTELLIGENCE BASED CLOSED LOOP GLUCOSE CONTROL SYSTEM AS A THERAPEUTIC MODALITY IN TYPE 1 AND TYPE 2 DIABETIC PATIENTS

Protocol IMT 2022-1

CONFIDENTIAL

Version1.0.7

22 August 2022

Subjects who volunteer for the study will have the study thoroughly explained to them during visit 2. Subjects who willingly volunteer for the study, after having all their questions answered, will sign an informed consent. Subjects who have signed an informed consent will be assigned a unique identification number that will remain the same throughout the study. Those subjects who have signed an informed consent and whose lab results obtained during visit 2 do not exclude them from the study, will proceed to visit 3, which must occur within 2 weeks of the date of enrollment. The following instructions will be given to the subjects in preparation for visit 3:

1. For subjects taking the SGLT-2 inhibitor Ertugliflozin, they will be instructed to stop taking this medication four days prior to visit 3.
2. For subjects taking the SGLT-2 inhibitors Canagliflozin, Dapagliflozin, and Empagliflozin, they will be instructed to stop taking these medications three days prior to visit 3.
3. For subjects taking sulfonylureas or meglitinides, they will be instructed to stop taking these medications after their morning doses on the day prior to visit 3 (e.g., if visit 3 starts on a Wednesday, the subjects will stop taking these medications after their morning doses on the previous day = Tuesday).
4. If usually taking long-acting insulin in the PM, then on the evening prior to visit 3:
 - a) Take half the usual evening dose of long-acting insulin if history of nocturnal hypoglycemia.
 - b) Take the full usual dose of insulin if no history of nocturnal hypoglycemia.
 - c) Insulin doses may also be adjusted at the discretion of the investigators (endocrinologists: [name] and [name]).
5. Subjects to fast after midnight on the evening prior to visit 3.
6. Subjects to not take any oral anti-hyperglycemic medications on the morning of visit 3.
7. After admission to the CRC on the morning of visit 3, all Reference Glucose Values and insulin administration will be performed by the clinical study staff of the CRC. Insulin dosing will be at the recommendation of adult endocrinologists ([name]) who are the principal investigators for this study. The dose of short acting insulin ordered after admission to the CRC will be based on the amount of carbohydrates ingested by the subjects for breakfast after their CRC admission, their Reference Glucose Value measured just prior to breakfast, and their usual home routine.

8.1.1.4 VISIT 3, TIME 0 TO 5 HOURS (PREPARATION FOR CLOSED LOOP GLUCOSE CONTROL STUDY)

1. General

All subjects will be admitted between the hours of 0600 to 0700 to a single patient CRC room large enough to hold the subject, study personnel and necessary equipment. The study equipment, at a

DEMONSTRATION OF AN ARTIFICIAL INTELLIGENCE BASED CLOSED LOOP GLUCOSE CONTROL SYSTEM AS A THERAPEUTIC MODALITY IN TYPE 1 AND TYPE 2 DIABETIC PATIENTS

Protocol IMT 2022-1

CONFIDENTIAL

Version1.0.7

22 August 2022

minimum should include a cardiac monitor, pulse oximeter, intermittent blood pressure capabilities, and a resuscitation cart.

2. Screening Prior to Initiation of the Closed Loop Glucose Control Session

The subjects will be tested for the presence of diabetic ketoacidosis and appropriate Reference Glucose Values prior to proceeding to steps 3-6 below. This testing will include:

- i. Reference Glucose Value at time of admission to the CRC – If the Reference Glucose Value is greater than 300 mg/dL, the subject will be screened for blood ketones using the Nova Max Plus (Nova Biomedical) ketone meter. If the Reference Glucose Value is less than 70 mg/dL or the subjects are experiencing any symptoms of hypoglycemia, regardless of their Reference Glucose Value, the subjects will be offered a snack or glucose containing juice. To be clear, the Nova Max Plus ketone meter will be used for any blood ketone analysis performed during the time the subjects are in the CRC.
- ii. Blood ketones – The study will be cancelled if the blood ketones are $> 1 \text{ mmol/L}$. If blood ketones are $> 1 \text{ mmol/L}$, a venous blood sample will be sent to the central lab at Emory University for a basic metabolic panel, venous pH and beta-hydroxybutyrate to rule out diabetic ketoacidosis. If diabetic ketoacidosis is confirmed, the subject will be stabilized per the usual routine care at Emory Healthcare.
- iii. Blood glucose prior to insertion of Dexcom G6 CGM's and intravenous lines – The subjects Reference Glucose Value must be in the range of 70-300 mg/dL prior to insertion of the two Dexcom G6 CGM's and two intravenous lines.

In addition, the closed loop glucose control session of the study will not be initiated if the participant has symptoms requiring action (e.g., abdominal pain, vomiting, unable to eat or drink, fever ≥ 101.5), regardless of blood glucose or ketone levels.

3. Dexcom G6 CGM devices

The subjects will have two Dexcom G6 CGM devices placed in the abdominal position, approximately 5 cm to the left or right of the umbilicus (Figure 25).

[figure not shown]

Figure 25 – Green shaded areas denote appropriate areas of the abdominal wall to place the Dexcom G6 CGM's. This figure is from the Dexcom G6 CGM user manual.

The CGM devices should be placed shortly after arrival to the CRC facility. For the Dexcom G6 CGM labeled "#1", enter the glucose sensors four-digit code and the transmitters six-digit serial number into the Dexcom G6 Receiver labeled "#1" and into the Dexcom G6 Follow App on the mobile phone labeled "#1". For the Dexcom G6 CGM labeled "#2", enter the glucose sensors four-digit code and the transmitters six-digit serial number into the Dexcom G6 Receiver labeled "#2" and into the Dexcom G6 Follow App on the mobile phone labeled "#2". Position the mobile phones 15-20 feet from the bed the subject will be using during the study.

4. Peripheral Intravenous Lines

For purposes of medication infusion, all subjects will have a peripheral IV placed into the antecubital vein of one arm. For purposes of blood removal, all subjects will have an IV placed in the contralateral hand in a retrograde position. The hand with the retrograde IV will be warmed to 50-55 degrees Celsius with a commercial warming box or warming pad for purposes of arterializing the venous blood.⁹⁰

5. Reference Glucose Value

After both Dexcom CGM's have started to return glucose values to the Dexcom Receivers, and prior to starting the closed loop glucose control portion of study, a Reference Glucose Value(s) (taken from arterialized retrograde hand IV line) will be measured using the Nova StatStrip Hospital Glucose Meter System. If the retrograde hand vein is no longer available at any point during visit 3, Reference Glucose Values may be obtained from a finger stick (capillary blood), with analysis of this sample being performed on the Nova StatStrip Hospital Glucose Meter System.

On July 12, 2018, the FDA cleared the Nova StatStrip Hospital Glucose Meter System for point of care capillary blood glucose monitoring for all hospital patients, specifically including those receiving intensive medical intervention therapy. According to the FDA's 510(k) Substantial Equivalence Determination Decision Summary Assay and Instrument Combination Template for this product, two

studies were performed. In the first study for blood glucose values less than 75 mg/dL, 1 of 1 specimen (100%) was compliant, and for blood glucose values greater than or equal to 75 mg/dL, 484/567 (85.4%) specimens were compliant. In the second study for blood glucose values less than 75 mg/dL, 1614/1894 (85.2%) specimens were compliant, and for blood glucose values greater than or equal to 75 mg/dL, 12799/14884 (86.0%) specimens were compliant.⁹¹

The Nova StatStrip Hospital Glucose Meter System has been cleared for use on arterial, venous, and capillary whole blood samples, and is currently used to guide intravenous insulin infusion rates in the ICU setting.

6. Calibration of Dexcom G6 CGM's

The Dexcom G6 CGM's will be calibrated under the following scenarios:

1. The Dexcom G6 CGM value(s) do not meet CGM Validation Criteria
If one or both of the Dexcom G6 CGM's are more than 20 mg/dL different from the Reference Glucose Value for CGM values less than 100 mg/dL, or are more than 20% different from the Reference Glucose Value for CGM values greater than or equal to 100 mg/dL at any time during visit 3, they will be recalibrated against the result from the Reference Glucose Value (using the Dexcom G6 receiver(s)). This calibration must occur within 5 minutes of obtaining the Reference Glucose Value sample. If the Dexcom G6 Receivers are recalibrated, the matching mobile phone's Dexcom App must also be recalibrated at the same time (e.g., if Dexcom Receiver #1 is recalibrated, also recalibrate the Dexcom G6 Follow App in mobile phone #1). If a Dexcom G6 sensor is recalibrated, a follow up CGM one hour after the recalibration must be within 20 mg/dL of the Reference Glucose Value for CGM values less than 100 mg/dL, or within \pm 20% of the Reference Glucose Value for CGM values greater than or equal to 100 mg/dL. If a CGM is felt to be inaccurate – cannot be calibrated to meet the aforementioned CGM Validation Criteria – it may be replaced according to the CGM Replacement Criteria.
2. The Dexcom G6 CGM's are greater than 20% different than their averaged value. If the averaged glucose value of the two Dexcom G6 CGM's is greater than 20% different than the CGM values, a Reference Glucose Value will be obtained and both CGM's will be re-calibrated against the result of the Reference Glucose Value using the Dexcom G6 receivers. This recalibration must occur within 5 minutes of obtaining the Reference Glucose Value sample. In this scenario, the FUSION system will automatically alert the clinical study staff of the need to recalibrate both Dexcom G6 CGM's. If the Dexcom G6 Receivers are recalibrated, the matching mobile phone's Dexcom Follow Apps must also be recalibrated at the same time. If a Dexcom G6 CGM is recalibrated, the CGM value one hour after recalibration must be within 20 mg/dL of the Reference Glucose Value for CGM values less than 100 mg/dL, or within \pm 20% of the Reference Glucose Value for CGM values greater than or equal to 100 mg/dL.

DEMONSTRATION OF AN ARTIFICIAL INTELLIGENCE BASED CLOSED LOOP GLUCOSE CONTROL SYSTEM AS A THERAPEUTIC MODALITY IN TYPE 1 AND TYPE 2 DIABETIC PATIENTS

Protocol IMT 2022-1

CONFIDENTIAL

Version1.0.7

22 August 2022

Prior to starting the closed loop glucose control session, a Reference Glucose Value will be obtained immediately after the time when the CGM sensors begin to return glucose readings. Reference Glucose Values will be subsequently checked every 30 minutes until the CGM sensor values meet the following CGM Validation Criteria:

1. CGM's must be within 20 mg/dL of the Reference Glucose Value for CGM values less than 100 mg/dL, or within \pm 20% of the Reference Glucose Value for CGM values greater than or equal to 100 mg/dL.

Closed-loop therapy will begin after two consecutive averages of CGM values meet the above CGM Validation Criteria. The above CGM Validation Criteria will be used throughout the entirety of visit 3.

Blood for independent glucose analysis will be drawn from the retrograde venous line in the warmed hand. The drawn blood will be immediately analyzed for glucose using the Nova StatStrip Hospital Glucose Meter System. These blood glucose values will be known as the Reference Glucose Values. If the arterialized venous line stops working, it may be replaced. If an arterialized venous line is no longer available, fingerstick capillary blood may be used for Reference Glucose Values. Fingerstick capillary blood will be analyzed using the Nova StatStrip Hospital Glucose Meter System.

All Reference Glucose Values will be manually recorded on the studies case report form, however, they will not be used by the FUSION system for purposes of glucose control (except to calibrate the Dexcom G6 CGM's, as necessary).

All subjects will be allowed to drink water throughout the course of the study. No glucose containing drinks will be allowed during the closed loop portion of the study, unless the subjects glucose level (CGM or Reference Glucose Value) is < 70 mg/dL, or the subject is experiencing symptoms of neuroglycopenia. Subjects will remain confined to either the bed or a bedside chair throughout the course of the study. Subjects will use a bedside commode for bathroom breaks in order to prevent any interruption to their closed loop glucose control session.

The following supplies will be needed to complete the study: **1)** four 4-way stopcocks, **2)** two IV tubing (non-microbore) of 6-12 foot length for purpose of attaching the glucose controllers syringe pumps to the subject, **3)** Forty 50 mL BD syringes filled with D10NS (study site research pharmacy to fill these 50 mL syringes using their standard sterile technique), **4)** Six 50 mL BD syringes filled with NovoLog insulin mixed in normal saline to a concentration of 1 unit/mL (study site research pharmacy to fill these 50 mL syringes using their standard sterile technique). The FUSION system (Figure 20) will be supplied by the study sponsor.

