4.3.10 RISK OF DIABETIC KETOACIDOSIS (DKA)

DKA is a metabolic condition brought on by lack of sufficient insulin supply such that the body can no longer use glucose as a fuel source, which leads to excessive breakdown of fat, and abnormal labs consisting of elevated blood levels of glucose and beta hydroxybutyrate, with a concomitant lowering of the blood pH. The risk of the participants entering the study while they are in DKA will be mitigated by screening for ketones at the time they are admitted to the CRC on visit 3. This screening will include a capillary blood Reference Glucose Value measured on the Nova StatStrip Hospital Glucose Meter System and blood ketone levels measured on the Nova Max Plus ketone meter (Nova Biomedical).

The risk of the subjects developing DKA while they are in the study will be mitigated by obtaining Reference Glucose Values at least every 1 hour. If the subjects CGM or Reference Glucose Value is > 240 mg/dL, the subjects will have their blood screened for ketones using the Nova Max Plus ketone meter. If the subject's blood ketone level is > 1 mmol/L, they will have venous blood sent for a basic metabolic panel, pH, and beta hydroxybutyrate to determine if they are in DKA. Subjects who are found to be in DKA, during their stay in the CRC during visit 3, will be removed from the study.

The benefit of testing the FUSION system on type 1 and type 2 diabetic subjects, whose blood glucose levels are difficult to control, outweighs the risk of the subjects developing DKA, given the information on the FUSION systems performance that will be gathered during the course of this study.

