| 7. | 
Screening prior to initiation of the closed loop glucose control session (time 0-1 hours)
 
The subjects will be tested for the presence of diabetic ketoacidosis and appropriate Reference Glucose Values prior to proceeding with the closed loop glucose control session. This testing will include:
 
i. Reference Glucose Value at time of admission to the CRC – If the Reference Glucose Value is greater than 300 mg/dL, the subject will be screened for blood ketones using the Nova Max Plus (Nova Biomedical) ketone meter. If the Reference Glucose Value is less than 70 mg/dL or the subjects are experiencing any symptoms of hypoglycemia, regardless of their blood Reference Glucose Value, the subjects will be offered a snack or glucose containing juice. To be clear, the Nova Max Plus ketone meter will be used for any blood ketone analysis performed during the time the subjects are in the CRC.ii. Blood ketones – The study will be cancelled if the blood ketones are $> 1 \text{ mmol/L}$. If blood ketones are $> 1 \text{ mmol/L}$, a venous blood sample will be sent to the central lab at Emory University for a basic metabolic panel, venous pH and beta-hydroxybutyrate to rule out diabetic ketoacidosis. If diabetic ketoacidosis is confirmed, the participant will be stabilized per the usual routine care at Emory Healthcare.iii. Blood glucose prior to insertion of Dexcom G6 CGM's and intravenous lines – The subjects Reference Glucose Value must be in the range of 70-300 mg/dL prior to insertion of the two Dexcom G6 CGM's and two intravenous lines. 
In addition, the closed loop glucose control session will not be initiated if the participant has symptoms requiring action (e.g., abdominal pain, vomiting, unable to eat or drink, fever ≥ 101.5), regardless of blood glucose or ketone levels.
 |

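### Section 4.3.10 describes an unconditional blood ketone screen at CRC admission, but the admission steps order the test only above 300 mg/dL, where insertion is already blocked

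*Combined protocol and SAP*

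**What the plan says.** Section 4.3.10 states that the risk of participants entering the study in DKA is "mitigated by screening for ketones at the time they are admitted to the CRC on visit 3". It then gives the content of the screen: "This screening will include a capillary blood Reference Glucose Value measured on the Nova StatStrip Hospital Glucose Meter System and blood ketone levels". Neither sentence has a glucose threshold. The next paragraph of 4.3.10 concerns DKA that develops during the study and adds a rule: "If the subjects CGM or Reference Glucose Value is > 240 mg/dL, the subjects will have their blood screened for ketones".

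The operative steps are in 8.1.1.4 item 2 and are repeated in Protocol 2 item 7. The lead-in of 8.1.1.4 reads: "The subjects will be tested for the presence of diabetic ketoacidosis and appropriate Reference Glucose Values prior to proceeding to steps 3-6 below". Three items follow.

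- Item i: "If the Reference Glucose Value is greater than 300 mg/dL, the subject will be screened for blood ketones". Below 70 mg/dL, or with symptoms of hypoglycemia, the subject is offered a snack or juice.
- Item ii, on blood ketones: "The study will be cancelled if the blood ketones are" above 1 mmol/L. Confirmatory laboratory work follows.
- Item iii: "The subjects Reference Glucose Value must be in the range of 70-300 mg/dL prior to insertion of the two Dexcom G6 CGM's" and the two IV lines.

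A closing sentence bars the start of the closed loop session in a subject with symptoms that need action, whatever the glucose or ketone level.

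**The concern.** The risk section relies on an admission ketone value. The steps that should produce it ask for one only at glucose above 300 mg/dL. Item iii already stops insertion there until glucose has come down. In the range where insertion may go ahead, item i asks for nothing, so the mitigation in 4.3.10 is not carried through to the bedside instructions.

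The population makes the screen worth getting right. Two of the eight subjects have type 1 diabetes and, in the synopsis's words paraphrased, make no insulin of their own. All subjects arrive fasting. Those with a history of nocturnal hypoglycemia who usually take long-acting insulin in the evening are told to take half that dose (8.1.1.3, instruction 4a).

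Section 9.2 criterion 3 ends the entire study if one subject has DKA after the session starts. An admission ketone value would help show whether ketosis was present before the device was used. The help is only partial, because the session begins about 5 hours after admission.

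**Working it through.** The plan gives no figure to reproduce. The check sets the thresholds side by side.

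**Inputs**
- Admission screen in 4.3.10: glucose and blood ketones, no glucose condition.
- Ketone trigger in 8.1.1.4 item 2.i and Protocol 2 item 7.i: above 300 mg/dL.
- Insertion range in item iii: 70-300 mg/dL.
- Cancellation rule in item ii: ketones above 1 mmol/L.
- Signs of DKA in 9.1 criterion 5 and Protocol 2 item 14.A criterion 5: Reference Glucose Value above 240 mg/dL and ketones above 1 mmol/L.
- Admission at 0600-0700; session start at about 1200.

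**Step 1: overlap of trigger and insertion range.** The trigger is > 300 and the range is 70 to 300. The overlap is empty.

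**Step 2: each admission band, with item i taken on its own**

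| Admission glucose (mg/dL) | Ketone test ordered by item i | Insertion allowed by item iii | Glucose part of criterion 5 met |
|---|---|---|---|
| Below 70 | No (snack or juice offered) | Once at 70 | No |
| 70-240 | No | Yes | No |
| 241-300 | No | Yes | Yes |
| Above 300 | Yes | Only once at 300 or below | Yes |

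The test is ordered in one band only, the one where insertion is blocked. It still has a use there, for a subject whose glucose later falls to 300 or below.

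**Step 3: the band that matters most.** Criterion 5 starts above 240 and item i above 300, so the width between them is 300 − 240 = 60 mg/dL (241-300). A subject in this band with ketones above 1 mmol/L meets the protocol's own definition of signs of DKA. Criterion 5 needs a ketone value but does not order one. At 240 or below it cannot be met, and only the item ii cancellation rule goes unused.

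**Step 4: does item ii order the test?** It says what to do with a result. It does not say who is tested.

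**Step 5: time from admission to session.** 1200 − 0700 = 5 hours; 1200 − 0600 = 6 hours.

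**Step 6: how many subjects.** The documents give no distribution of admission glucose or ketones. The number who would go untested under item i alone can only be bounded, at 0 to 8.

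**The case against.** A reader might infer that a subject at 241-300 mg/dL will reach the closed loop session with no ketone value, possibly in DKA. The documents do not support that.

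- **The 240 mg/dL rule.** The second paragraph of 4.3.10 orders a ketone screen at any CGM or Reference Glucose Value above 240 mg/dL. It opens with DKA developing during the study, but its removal rule reaches subjects found in DKA at any time during the visit 3 stay, which begins at admission. It arguably covers 241-300 already. The discretionary ketone wording in Protocol 2 (Potential Problems) applies only while FUSION is running, so it does not weaken the rule before the session.
- **The lead-in and item ii.** Protocol 2 item 7 opens "The subjects will be tested for the presence of diabetic ketoacidosis" and lists blood ketones as its own item. That can be read as testing everyone, in line with 4.3.10.
- **What is reached untested.** It is the placing of two sensors and two IV lines, 5 to 6 hours before closed loop control. In between, the investigators set a breakfast insulin dose from a Reference Glucose Value, and glucose is checked every 30 minutes from the first CGM readings until the sensors validate. Subjects with symptoms needing action cannot start.
- **Signs of DKA are not DKA.** The adverse event definition in 10.3.3.1 requires symptoms, ketones above 1.5 mmol/L and an abnormal pH or bicarbonate. An asymptomatic subject with ketones just above 1 mmol/L does not meet it.
- **Preparation for visit 3.** Subjects without nocturnal hypoglycemia take the full evening dose, the investigators may adjust doses, and SGLT-2 inhibitors are stopped three or four days ahead.

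Most of this stands, and it limits the consequence. It does not remove the conflict. If everyone is tested, the 300 mg/dL condition in item i is redundant. The 240 mg/dL rule does not appear in either set of admission steps, which give 300 instead. Two careful nurses could follow the same page and act differently.

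**Conclusion.** The conflict holds and lies in current text. Section 4.3.10 describes an admission ketone measurement without condition. The two operative lists order it only above 300 mg/dL, outside the 70-300 mg/dL range that permits insertion. As a result the cancellation rule in item ii may have no value to act on.

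The severity is minor. No endpoint, estimate or sample size is affected. The band table in the working rests on item i being followed alone; under either of the two softer readings, some or all of the untested subjects would be tested. How often the gap would matter cannot be estimated from the documents.

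**What to change.** In 8.1.1.4 item 2.i and Protocol 2 item 7.i, replace the sentence carrying the 300 mg/dL condition with: *All subjects will have a Reference Glucose Value and a blood ketone level (Nova Max Plus) measured at admission to the CRC.* Keep the snack instruction for low glucose or symptoms. Leave items ii and iii and Section 4.3.10 unchanged.

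**Cost.** One sentence in two places. Extra strips: at most 8 subjects × 1 = 8, plus one for each replacement. The ketone meter and strips are already on the Protocol 1 materials list. Testing everyone also extends the 1 mmol/L cancellation rule to fasting subjects at 70-240 mg/dL, so an occasional visit 3 may be cancelled. Section 9.2 allows a subject who has consented but not received closed loop control to be replaced.

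**Narrower alternative.** Changing 300 to 240 in both items would close the 241-300 band with fewer tests and cancellations. It would still differ from the unconditional screen in 4.3.10, which would then need rewording. The choice between them is clinical; the first makes the steps match what the risk section already says.
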